2.2. Randomization Methodology

Randomization will be performed via a centralized IWRS. Subjects will be randomized on Day 1 to one of three treatment groups in a 1:1:1 ratio for linzagolix 75 mg, linzagolix 200 mg with ABT and placebo.

Subjects will be randomized into permutated blocks of a pre-determined length.

Subjects participating in the extension phase and who are in the placebo treatment group will be randomized at the Month 6 visit to either linzagolix 75 mg or linzagolix 200 mg with ABT in a 1:1 ratio. Subjects participating in the extension phase and who are in the linzagolix treatment groups will remain on the same dose that they were taking at the end of Month 6 and will undergo a dummy randomization in order to maintain the blind.

There will be no stratification.

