2.5.1.2. Ranked Secondary efficacy endpoints

Ranked secondary efficacy endpoints (in the order of the endpoints to be tested) are:

- Change from baseline to Month 6 in DYS (VRS)
- Change from baseline to Month 6 in NMPP (VRS)
- Change from baseline to Month 6 in dyschezia (Numeric Rating Scale NRS)
- Change from baseline to Month 6 in overall pelvic pain (NRS)
- Change from baseline to Month 6 in the interference of pain with the ability to perform daily activities, measured using the pain dimension of the Endometriosis Health Profile-30 (EHP-30)
- Change from baseline to Month 6 in dyspareunia (VRS)
- No analgesics use for EAP during the preceding 4-week period at Month 6
- No opiate use for EAP during the preceding 4-week period at Month 6

Additional details on ranked secondary endpoints and analyses are provided in Section 4.6.

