4. STATISTICAL METHODS

4.1. Sample Size Justification

The planned sample size for this study is 150 subjects per treatment group (450 subjects in total).

An overall two-sided type I error of 0.05 will be used. As there are two linzagolix versus placebo comparisons, Bonferroni corrected p-values will be produced (raw p-values will be multiplied by two prior to comparing to 0.05). The planned sample size considers the hierarchical, fixed sequence testing of the ranked secondary endpoints as well as the co-primary endpoints. The assumptions used for the sample size calculations are based on analyses of clinically meaningful reduction in pain with a stable or decreased use of analgesics from the Phase 2b Edelweiss study. Calculations were performed using East[®] 6.5 software.

One hundred and fifty (150) subjects per treatment group will provide a power greater than 95% to reject the null hypothesis for both co-primary endpoints for either treatment group, assuming a placebo response rate of 14.6% and an active treatment response rate of 48.6% (75 mg, Edelweiss Phase II study results) or 64.7% (200 mg, Edelweiss Phase II study result) for DYS, and a placebo response rate of 18.8% and an active treatment response rate of 42.1% (75 mg, Edelweiss Phase II study result; the response rate for 200 mg in Edelweiss was lower but was inconsistent with the other doses and other timepoints for the same dose and so was not used) for NMPP. In addition, 150 subjects per treatment group provides 85% power to reject the null hypotheses for all the ranked secondary endpoints based on the observed results from the placebo and 200 mg treatment group in the Edelweiss study.

The values used for the sample size calculations assume that these responses rates are what would be seen on average when under treatment including taking into account any subjects who might withdraw from treatment early; therefore the calculations do not need to be further adjusted for dropouts.

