4.2. General Statistical Methods and Data Handling

4.2.1. General Methods

All output will be incorporated into Microsoft Excel or Word files, sorted and labeled according to the International Conference on Harmonisation (ICH) recommendations, and formatted to the appropriate page size(s).

Tabulations will be produced for appropriate demographic, baseline, efficacy, pharmacokinetic and safety parameters.

For continuous data and for ordered categorical data, if appropriate, the number of non-missing observations, mean, standard deviation, median, first and third quartiles, minimum and maximum will be calculated, including for change from baseline when applicable. The baseline mean will be calculated

Sponsor:	ObsEva		
Protocol:	18-OBE2109-003		
Document Version No.:	V5.0		

for all subjects based on the FAS. For efficacy endpoints and BMD, a baseline mean will also be calculated for each visit using the baseline data for the subset of subjects who attended that visit, such that the same subjects contribute to the mean for the visit and the mean for the corresponding baseline values. Summary statistics will be based primarily on non-missing values. For ordered categorical data and nominal data, absolute counts and relative frequencies (in %) will be calculated.

This study will be conducted at approximately 100 study sites, resulting in only a few subjects per site on average. Subjects from all sites will be pooled and no adjustment for sites will be carried out in the statistical analyses.

Raw and derived data will be listed.

All statistical hypothesis tests and confidence intervals will be two sided.

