4.2.5. Multiple Comparisons/Multiplicity

All statistical hypothesis tests and confidence intervals will be two-sided. To maintain an overall type I error rate of 0.05, as there are two linzagolix versus placebo comparisons, Bonferroni corrected p-values will be produced (raw p-values will be multiplied by two prior to comparing to 0.05), along with corresponding 97.5% confidence intervals.

The two co-primary efficacy endpoints will be clinically meaningful reduction from baseline over the last 28 days of randomized treatment up to the Month 3 visit (i.e., the 4-week period preceding the Month 3 visit) in the mean daily assessment of DYS and of NMPP measured on a VRS, along with a stable or decreased use of analgesics for EAP.

The primary objective will be assessed by testing the following two-sided hypotheses for each co-primary endpoint, for each linzagolix group versus placebo separately:

Null hypothesis (H0): There is no difference in the odds of subjects meeting the primary endpoint for the active treatment group compared to placebo, that is, the odds ratio (OR) equals 1.

Sponsor:	ObsEva		
Protocol:	18-OBE2109-003		
Document Version No.:	V5.0		

H0: OR =1

Alternative hypothesis (H1): There is a difference in the odds of subjects meeting the primary endpoint for the active treatment group compared to placebo, that is, the OR is not equal to 1.

H1: OR ≠ 1

Where odds are equal to the proportion of subjects meeting the endpoint divided by proportion of subjects not meeting the endpoint.

Each linzagolix group will need to demonstrate a statistically significant difference for both co-primary endpoints for the group to be considered more efficacious than placebo, thus maintaining an overall type I error rate of 0.05.

For each linzagolix group that is statistically significantly more efficacious than placebo for the co-primary endpoints, a fixed-sequence testing strategy shall be used within the group to test the ranked secondary endpoints as ordered in Section 2.5.1.2, to maintain the family-wise type I error rate. That is, the comparison for each linzagolix group versus placebo for each ranked endpoint will only be declared statistically significant different if the raw p-value multiplied by two is less than or equal to 0.05 for that endpoint and for all preceding endpoints for that dose versus placebo.

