4.6.2.1.2. Primary Efficacy Analysis

The primary efficacy analysis will be conducted using the FAS.

The analysis of each co-primary endpoint will be conducted using a logistic regression model, with treatment group as the main effect (three values) and including the baseline pain score as a covariate. Individual linzagolix versus placebo treatment group comparisons will be made using the same logistic regression model. Estimated odds-ratios and 97.5% intervals of proportions of responders of linzagolix treatment groups versus placebo will be presented, along with Bonferroni corrected p-values. Estimates of proportions of responders with 95% confidence intervals will be presented as well, estimated at the overall mean baseline pain score.

SAS Code (may be updated at analysis stage to fit the data):

```
PROC LOGISTIC data=dataset order=internal;
Class treatment(ref=placebo) / param=glm ;
Model resp(event= "Yes")= treatment base_pain /alpha=0.05;
Oddsratio treatment ;
Lsmeans treatment / ilink exp cl alpha=0.05 at means diffs=control('1')
adjust=bon;
Ods output OddsRatiosWald=or ModelANOVA=ma ParameterEstimates=pe
lsmeans=lsm diffs=diffs;
```

Run;

In addition, the mean pelvic pain scores for DYS and NMPP and change from baseline for the last 28 days prior to Month 3 or the last 28 days of treatment (or less) for subjects who discontinued will be summarized as continuous variables by treatment group. Cumulative distribution functions (CDF) for change from baseline at Month 3 for DYS and NMPP will be provided, with separate lines for each treatment group. The x-axis will present the different values for the DYS or NMPP change from baseline, and the y-axis will present the proportion of subjects reaching each value of change. Vertical lines of the relevant MCT thresholds obtained at the Month 3 responder threshold analysis will be displayed on the plots.

The number and percentage of subjects with:

- Reduction of X for DYS,
- Reduction of X for NMPP,

Sponsor:	ObsEva		
Protocol:	18-OBE2109-003		
Document Version No.:	V5.0 Document Date: 13-JUN-2022		

- Stable or decreased use of analgesics for EAP during bleeding days, during non-bleeding days, and overall,
- Reduction of X for DYS and stable or decreased use of analgesics for EAP (during bleeding days),
- Reduction of X for NMPP and stable or decreased use of analgesics for EAP (during non-bleeding days),

will be presented.

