The analysis of the proportion of subjects reporting no analgesic use for EAP, and the proportion of subjects reporting no opiate use for EAP during the preceding 4-week period at Month 6 (last 28 days prior to and including last treatment administration date) will be conducted using a logistic regression model, with treatment group as the main effect (three values).

In addition to analgesic use for EAP as collected in the eDiary, concomitant medications in the study will be reviewed and medications to be considered as analgesic use for endometriosis associated pain will be confirmed by the Sponsor and be provided in an excel file prior to Database Lock. They may include any

Sponsor:	ObsEva		
Protocol:	18-OBE2109-003		
Document Version No.:	V5.0	Document Date:	13-JUN-2022

medication with the ATC codes from WHO drug dictionary version March 2016 as listed in Table 6 in Section 4.6.2.2.

In addition to analyzing the absence of analgesic use for EAP, the amount used for each 4-week period up to Month 6 will be summarized as a continuous variable, including the change from baseline. This analysis will be based on e-diary data only, as subjects did not record opioid intake in the concomitant medication page on a tablet-by-tablet basis.

As it is likely that more than one opioid will be used (opioid analgesic may be different depending on countries), the amount of opioid used will be converted to morphine milligram equivalents (MME) in order to better quantify the actual amount of opioids used by subjects.

For countries (Spain, Hungary, France, Czech Republic) where several opioids with different MME were allowed, the data collected in the e-diary is not sufficient to determine exactly which opioid was used and what the MME is. The MME will be derived as the average of possible MME of the allowed opioids in the country.

No opioids are allowed in Ukraine. Subjects from Ukraine will therefore be excluded from the summary in MME. If some opioids are nevertheless recorded for subjects from Ukraine, they will not be considered for the summary in MME, as the conversion in MME would be unknown. Those opioids records will however be considered for other analgesic use analyses not requiring conversion in MME.

The baseline amount of analgesic used will be computed by averaging the amount used during the two baseline menstrual cycles.

Conversion to MME by country is described in Table 7.

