4.6.4.5. Change from baseline to each scheduled assessment in mean daily dyspareunia scores

Sponsor:	ObsEva		
Protocol:	18-OBE2109-003		
Document Version No.:	V5.0	Document Date:	13-JUN-2022

reported during the previous 4-week period on the dyspareunia VRS

The actual value and change from baseline in mean daily dyspareunia scores will be summarized as a continuous variable for each 28-day period. An analysis of covariance will be performed for each period.

Subjects not sexually active for reasons other than endometriosis will have missing values for the corresponding 4-week periods. Subjects not sexually active for reasons other than endometriosis at baseline will be excluded from the analysis.

4.6.4.6. Change from baseline to each scheduled assessment in mean daily dyschezia scores reported during the previous 4-week period assessed on the dyschezia NRS

The actual value and change from baseline in mean daily dyschezia scores will be summarized as a continuous variable for each 28-day period. An analysis of covariance will be performed for each period.

4.6.4.7. Change from baseline to each scheduled assessment in non-opioid, opioid and combined analgesic use for EAP during the previous 4-week period based on pill count in the eDiary

Non-opioid, opioid and combined analgesic use for EAP will be measured using the mean of daily pill count collected in the eDiary over each 28-day period. For non-opioid and combined analgesic use, descriptive summary (actual values and changes from baseline) and analysis of covariance for each period will be performed. Due to a low number of subjects using any opioids, opioids use will not be analyzed as a continuous variable, only a listing with by subject opioid use mean daily pill count will be provided.

The number and percentage of subjects reporting no analgesic use for EAP, and the proportion of subjects reporting no opiate use for EAP at baseline and during the preceding 4-week period at Month 3 (last 28 days prior to and including last treatment administration date) will be presented. The proportion of subjects with no analgesic use for EAP, and with no opiate use for EAP will be conducted using a logistic regression model, with treatment group as the main effect. For these proportions, in addition to eDiary analgesic use, data from the concomitant medication page will be used, as described in Section 4.6.3.6.

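### Ranked endpoint 8 (no opiate use at Month 6) has no stated test statistic or sparse-cell rule, and the inferred Wald test cannot succeed if an active arm has no opiate users

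*SAP*

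**What the plan says.** The eighth and last ranked secondary endpoint is "No opiate use for EAP during the preceding 4-week period at Month 6" (SAP 2.5.1.2). A dose succeeds on it only "if the raw p-value multiplied by two is less than or equal to 0.05 for that endpoint" and for every endpoint before it (SAP 4.2.5), which is a raw two-sided threshold of 0.025 per dose.

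SAP 4.6.3.6, like protocol 13.5.3.6, states that the analysis "will be conducted using a logistic regression model, with treatment group as the main effect (three values"). It gives no code, test statistic, interval method or provision for an empty cell.

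Logistic code appears in SAP 4.6.2.1.2 (co-primary analysis) and 4.6.5.2 (multiple imputation). Both request Wald quantities. The primary code outputs Wald odds ratios and takes the dose contrasts from "Lsmeans treatment / ilink exp cl alpha=0.05 at means diffs=control('1", which in a logistic fit are Wald comparisons; 4.6.5.2 pools Wald chi-squares.

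On opioid pill counts, SAP 4.6.4.7 says: "Due to a low number of subjects using any opioids, opioids use will not be analyzed as a continuous variable". Sections 4.6.4.8 and 4.6.4.10 reduce the MME and opioid-day endpoints to listings for the same reason. The V3.0 entries in SAP section 5 record these removals and, in the same row, add a proportion analysis at Month 3.

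**The concern.** With treatment as the only term, each dose-versus-placebo comparison is the log odds ratio of a 2×2 table. If no woman in one linzagolix arm uses an opiate, that log odds ratio has no finite maximum-likelihood estimate and its standard error diverges. A Wald test then fails exactly when the observed effect is as large as it can be.

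The SAP already describes opioid use as rare, so an empty cell is foreseeable. Women from Ukraine, where no opioid is permitted, are excluded only from the MME summary. They stay in this analysis and make users rarer still.

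At stake is a formally tested claim for each dose. Choosing a fallback after seeing the empty cell would be a data-driven change to a confirmatory test.

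**Working it through.** **Inputs from the SAP.** "The planned sample size for this study is 150 subjects per treatment group (450 subjects in total") in section 4.1; 1:1:1 allocation (2.2); two-sided tests (4.2.1); raw threshold 0.025 per dose (4.2.5).

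**Inputs assumed.** All opiate-user counts and rates below, because the documents give none.

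**The plan's own figures.** With 150 per arm and two-sided 0.025, NMPP at 18.8% versus 42.1% has 98.7% power. DYS at 14.6% versus 48.6% exceeds 99.99%. Joint power for both co-primaries is 98.7%, so the stated figure above 95% reproduces. The 85% for all ranked secondaries cannot be checked, because the rates and SDs behind it are not given.

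**Formulas**, with a users of 150 on active and b of 150 on placebo:
- Wald: z = ln{[a/(150−a)] / [b/(150−b)]} / √[1/a + 1/(150−a) + 1/b + 1/(150−b)].
- Pearson score: X² = 300·[a(150−b) − b(150−a)]² / [150·150·(a+b)·(300−a−b)].
- The unstratified CMH statistic is X²·299/300, so it is nearly identical.

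**Zero users on active.** The term 1/a is undefined. For 0 versus 10, a Newton fit gives p of about 0.42 after 8 steps (log odds ratio 6.6 in magnitude, SE 8.1) and 0.96 after 15 (13.6, SE 269). The printed value depends on where iteration stops. Score p is 0.0013 and Fisher p 0.0017 on the same data. For 0 versus 8, X² = 300·(8·150)²/(22500·8·292) = 8.22, giving p=0.004; Fisher gives 0.007. Against an empty active arm the score test is significant from 5 placebo users (p=0.024) and Fisher from 7 (p=0.0145). Wald never is.

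**One or two users on active.**

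| Active vs placebo | Wald | Score | Fisher |
|---|---|---|---|
| 1 vs 7 | 0.065 | 0.032 | 0.067 |
| 1 vs 8 | 0.046 | 0.018 | 0.036 |
| 1 vs 9 | 0.034 | 0.010 | 0.0195 |
| 1 vs 10 | 0.02504 | 0.006 | 0.010 |
| 1 vs 11 | 0.019 | 0.003 | 0.005 |
| 2 vs 9 | 0.0495 | 0.032 | 0.061 |
| 2 vs 10 | 0.0336 | 0.018 | 0.0349 |
| 2 vs 11 | 0.023 | 0.011 | 0.0197 |

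For 1 versus 9, the log odds ratio is −2.25 and the SE 1.06, so z = −2.12. With one user, Wald loses to the score test at 8, 9 and 10 placebo users. With two users it loses only at 10, and there Fisher fails as well.

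**Chance of an empty arm**, (1−r)^150: 47% at r=0.5%, 22% at 1%, 5% at 2%.

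**Exact power at 0.025, assumed rates:**

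| Placebo vs active | Wald | Score | Fisher |
|---|---|---|---|
| 5% vs 0.5% | 7% | 61% | 43% |
| 8% vs 0.5% | 34% | 92% | 86% |
| 10% vs 1% | 66% | 94% | 90% |
| 10% vs 3% | 53% | 61% | 51% |
| 15% vs 3% | 92% | 95% | 92% |

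**Size under the null**, common rates 1% to 10%: Wald 0.0000 to 0.021, score 0.008 to 0.025, Fisher 0.0004 to 0.015. The likelihood-ratio test runs from 0.028 to 0.044, above the threshold, so it is not a safe substitute.

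**The case against.** Section 4.6.3.6 does not name Wald. The code quoted belongs to the co-primary analysis, has a baseline covariate and is marked as open to updating. That stands: Wald is an inference from the SAP's only logistic code, and the gap is an unspecified test. It does not remove the problem, because following the stated model in the SAP's usual way gives a Wald contrast.

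The statement that users are few concerns eDiary opioid use and is not split by arm. Endpoint 8 also counts concomitant medications confirmed by the sponsor, so its user count may be larger. That stands too; how likely an empty arm is cannot be determined from the documents.

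Replacing models of amount with a proportion is a sensible response to few users. Agreed: the omission is only that the proportion was left without a sparse-cell rule.

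A reader might infer that Wald is generally inferior whenever users are rare. The tables do not show that. With two users, Wald and Fisher reach the same decision, and at 10% or 15% versus 3% their power is about equal.

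A reader might also infer that the 85% power claim is wrong. Since Wald power cannot exceed 1−(1−r)^150, it falls short of 85% when the on-drug rate r is below 1−0.15^(1/150) = 1.26%. The documents do not give that rate, so the claim is unverified, not refuted.

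**Conclusion.** The point holds as a should-fix. A confirmatory test is left without a statistic or sparse-cell rule, and its inferred default cannot succeed if an active arm has no opiate users. Beyond the empty cell, the loss against the score test is confined to a narrow band at one user and, with two users, to a single placebo count. These results assume 150 analysed per arm and a Wald contrast; every user count and rate is illustrative.

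It would be tempting to treat this as a threat to the trial's main conclusions. The documents do not support that. Endpoint 8 is reached only after both co-primaries and seven ranked endpoints succeed for that dose, and nothing follows it. Wald errs on the conservative side here, so type I error is not inflated. Month 3 lies outside the fixed sequence, and the Per Protocol repeat is supportive. The harm is lost power and an unusable odds ratio and interval for this one endpoint.

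**What to change.** Before unblinding, add to SAP 4.6.3.6 that for no opiate use at Month 6 each pairwise p-value comes from the Pearson/CMH score test already coded in 4.6.2.2, doubled as in 4.2.5, regardless of the observed counts. Report the odds ratio and 97.5% confidence interval from Firth-penalised logistic regression with profile penalised likelihood. Use the same method for the nominal Month 3 analysis in 4.6.4.7 and the Per Protocol repeat, for consistency. Endpoint 7 (no analgesic use) needs no cell-count switch: nothing in the documents suggests it is sparse, and such a switch would make the test depend on the data.

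The cost is one or two sentences and one model option. The Firth odds ratio is slightly shrunken, and because the p-value and interval come from different methods they may occasionally disagree at the margin.

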4.6.4. Additional Secondary Endpoints

All additional efficacy endpoints will be summarized by descriptive statistics for each treatment group, for each time point, including summaries of change from baseline when applicable. Individual linzagolix versus placebo treatment group comparisons will be made.

In general, between group comparisons for continuous endpoints will be analyzed via analysis of (co)variance. Between-group comparisons for binary endpoints will be analyzed via logistic regression. Between-group comparisons for ordinal categorical data will be analyzed using a Mantel-Haenszel test, or using Koch's method when there is also a baseline covariate.

As described in section 4.2.5 additional secondary endpoints will use Bonferroni correction for p-values of comparison of treatment groups at each visit. The analyses do not form part of the fixed-sequence strategy being used for the ranked secondary endpoints and will not be fully controlled for an overall type I error rate.

Values for all endpoints that are collected daily using the eDiary (from Section 4.6.4.1 to Section 4.6.4.18) will be based on the 28 calendar days immediately prior to and including the day of the corresponding visit or prior to and including the last treatment administration date for Month 6, or the 28 calendar days immediately prior to and including the last dose date for subjects who discontinue treatment prior to the visit in question (or fewer if treatment is stopped less than 4 weeks after first dose date), in order to estimate the treatment effect while under treatment. The last 28 days on treatment will be used at all subsequent scheduled visits for those discontinued subjects. Descriptive summaries for each 28-day period will be performed in two ways however:

- Once including only values of 28 days prior to Month X, i.e. using the last 28 days prior to Month X eCRF visit date for subjects who have not discontinued up to that month. If subjects discontinued prior to Month X the corresponding value will be missing from the summary at Month X;
- Once applying the while on treatment strategy, i.e. using the last 28 days prior to Month X eCRF visit date for subjects who have not discontinued up to that month, and for subjects who discontinued prior to Month X, the last 28 days prior to treatment discontinuation will be used. For all subsequent timepoints (Month X+1, etc.) the same last 28 days prior to treatment discontinuation will be used.

Corresponding baseline values will be calculated based on the two baseline menstrual cycles, which may not be exactly 28 days each.

The values for other endpoints (monthly and 3-monthly questionnaires from Section 4.6.4.19 to Section 4.6.4.26) are defined as the value at the corresponding visit or value falling into the corresponding visit window as described in section 4.2.9. For these other endpoints, descriptive summaries by visit will be

Sponsor:	ObsEva		
Protocol:	18-OBE2109-00	3	
Document Version No.:	V5.0	Document Date:	13-JUN-2022

performed in two ways, once including values at the corresponding visit or value falling into the corresponding visit window as described in section 4.2.9, and once applying the while on treatment strategy, i.e., including values from the discontinued visits at each next scheduled visit.

For endpoints based on daily diary data, analyses will use observed data only in such cases, provided that a minimum number of 43% (at least 12 days of each 28-day period) completed daily eDiary entries are available.

4.6.4.1. Clinically meaningful reduction at scheduled visits other than Month 3 for DYS and NMPP

The proportion of responders for DYS and NMPP based on daily e-diary data will be reported at each visit (each 28 days period) along with odds-ratio and 97.5% confidence intervals from logistic regression as described in Section 4.6.2.1.2.

The same responder definition defined for primary endpoint in Section 4.6.2.1.1 will be used, but for other scheduled visits.

Due to the war situation in Ukraine, data from subjects in Ukraine sites may be incomplete, missing or uncleaned. The descriptive analysis of proportion of responders for DYS and NMPP at each visit will be repeated, excluding data collected after 24FEB2022 for subjects from Ukraine sites, for the Follow-up period only (Follow-up set), as the main treatment period was completed before the start of the war. Listings will contain country information to identify those subjects.

4.6.4.2. Change from baseline to each scheduled assessment in mean pelvic pain scores for DYS, NMPP and overall pelvic pain, during the previous 4-week period assessed on the NRS and VRS

The change from baseline to each scheduled assessment in mean pelvic pain scores for DYS, NMPP and overall pelvic pain will be analyzed as described for the ranked secondary endpoint in Section 4.6.3.1 (continuous summary and analysis of covariance at each visit).

4.6.4.3. Change from baseline to each scheduled assessment in the number of days with moderate to severe pelvic pain during the previous 4-week period assessed on the VRS

The actual value and change from baseline of number of days with moderate or severe pelvic pain collected in the e-diary on the VRS will be summarized for each 28-day period. The baseline value will be computed by averaging the number of days with moderate or severe pelvic pain of the two baseline menstrual cycles. The number of days will be analyzed with a negative binomial model including baseline

Sponsor:	ObsEva		
Protocol:	18-OBE2109-003		
Document Version No.:	V5.0	Document Date:	13-JUN-2022

as a covariate. The estimated least square means treatment differences along with 97.5% CI will be provided.

SAS Code for negative binomial model with repeated measurements

```
proc genmod data=dataset order=internal ;
    class treatment;
    model nbdays = baseline treatment / dist=negbin type3 ;
    lsmeans treatment / diff = control('1') exp at means cl alpha=0.05
adjust=bon;
estimate 'TRT Placebo' intercept 1 base %sysevalf(&meanbase.) trt01pn 1 0 0 /
exp E;
estimate 'TRT LGX 75' intercept 1 base %sysevalf(&meanbase.) trt01pn 0 1 0 /
exp E;
estimate 'TRT LGX 200' intercept 1 base %sysevalf(&meanbase.) trt01pn 0 1 0 /
exp E;
estimate 'TRT LGX 200' intercept 1 base %sysevalf(&meanbase.) trt01pn 0 1 0 /
exp E;
estimate 'TRT LGX 200' intercept 1 base %sysevalf(&meanbase.) trt01pn 0 0 1
/ exp E;
    ods output lsmeans=lsm diffs=lsmd Estimates=estimate ;
```

run;

"meanbase" macro variable is the mean value of baseline over the same selection of subjects used in the model

4.6.4.4. Change from baseline to each scheduled assessment in the mean worst pelvic pain score defined as the mean of the 5 highest daily pain scores reported during the previous 4-week period assessed on the NRS

The actual value and change from baseline of the mean worst pelvic pain score, defined as the mean of the 5 highest daily pain scores reported during each 28-day period will be summarized for each 28-day period. The baseline mean worst pelvic pain score will be the average of the mean pelvic pain score of each of the two baseline menstrual cycles. An analysis of covariance will be performed for each period.

If less than 5 days of pain score data is available, the mean worst pelvic pain will be defined as the mean of the available daily pain scores.

